AST	Aspartate aminotransferase
ATC	Anatomical Therapeutic Class
ATTR	Amyloid transthyretin
BMI	Body mass index
CEC	Clinical events committee
CI	Confidence interval
CSR	Clinical study report
CTCAE	Common Terminology Criteria for Adverse Events
CV	Cardiovascular
DB	Double blind
DMC	Data monitoring committee
CCI	
eCRF	Electronic case report form
CCI	
FAS	Full Analysis Set
hATTR	Hereditary ATTR
HF	Heart failure
HLT	High level term
HR	Hazard ratio
ICH	International Council for Harmonisation
IRT	Interactive response technology
ISR	Injection site reaction
JFM	Joint frailty model
KCCQ-OS	Kansas City Cardiomyopathy Questionnaire-Overall Summary

Abbreviation	Definition
LFT	Liver function test
LS	Least square
LV	Left ventricular
LVAD	Left-ventricular assist device
MAR	Missing at random
MCMC	Markov Chain Monte Carlo
MedDRA	Medical Dictionary for Regulatory Activities
MI	Multiple imputation
MLE	Maximum likelihood estimates
MMRM	Mixed effects model repeated measures
MNAR	Missing not at random
CCI	[REDACTED]
NT-proBNP	N-terminal prohormone B-type natriuretic peptide
NYHA	New York Heart Association
OLE	Open Label Extension
PD	Pharmacodynamic
PK	Pharmacokinetic
PMM	Pattern mixture model
CCI	[REDACTED]
PT	Preferred term
Q1, Q3	First quartile, third quartile
q3M	once every 3 months
REML	Restricted maximum likelihood
SAE	Serious adverse event
SAF	Safety Analysis Set
SAP	Statistical analysis plan
SD	Standard deviation
SE	Standard error
SMQ	Standardized MedDRA query
SOC	System organ class
TEAE	Treatment-emergent adverse event
TTR	Transthyretin

Abbreviation	Definition
SUSAR	Suspected Unexpected Serious Adverse Reaction
ULN	Upper limit of normal
wtATTR	Wild type ATTR

1. INTRODUCTION

This statistical analysis plan (SAP) details comprehensive specifications of the efficacy, safety, pharmacodynamic (PD), and pharmacokinetic (PK) data summaries and statistical analyses in support of the clinical study report (CSR) for Study ALN-TTRSC02-003 (HELIOS-B). Changes to planned analyses specified in the final SAP made after database lock will be documented with justification in the CSR.

Table, figure, and listing mock shells and specifications are contained in separate documents.

Unless otherwise specified, statistical analyses will be conducted using SAS software Version 9.4 or newer.

2. STUDY DESIGN

2.1. Synopsis of Study Design

This is a Phase 3, randomized (1:1), double-blind, placebo-controlled, multicenter study to evaluate the efficacy and safety of vutrisiran in approximately 600 patients with transthyretin (TTR) amyloidosis (ATTR amyloidosis) with cardiomyopathy. Approximately 20% of the study population is anticipated to have hereditary ATTR (hATTR) amyloidosis with cardiomyopathy and 80% to have wild type ATTR (wtATTR) amyloidosis with cardiomyopathy.

At study entry, patients are either:

- Not on tafamidis (tafamidis-naïve; see protocol for definition); or
- On tafamidis (currently receiving tafamidis) (Note: must be on-label use of commercial tafamidis per an approved cardiomyopathy indication and dose in the country of use).

The study consists of 4 periods ([Figure 1](#)):

1. **Screening Period:** Up to 45 days during which patients will undergo screening assessments to determine eligibility.
2. **Double-Blind Period (DB Period):**
 - At the start of the DB Period (on Day 1), eligible patients will be randomized in a 1:1 ratio to receive blinded doses of 25 mg of vutrisiran or placebo administered as a subcutaneous (SC) injection once every 3 months (q3M; every 12 weeks \pm 7 days) for up to 36 months.
 - An individual patient's DB Period visits will end after they complete their Month 36 visit, or 30 months after the last patient is randomized, whichever comes first. As such, a patient's last visit during the DB Period may vary from 30 to 36 months after enrollment.
 - The variable length of the DB Period will mean that some patients will not have a Month 33 and/or Month 36 visit. For patients whose last visit in the DB Period was Month 30 (Week 132), Day 1 in the OLE Period will occur 144 weeks (\pm 7 days) after enrollment in the DB Period. For patients whose last visit in the

DB Period was Month 33 (Week 144), Day 1 in the OLE Period will occur 156 weeks (± 7 days) after enrollment in the DB Period. For patients whose last visit in the DB Period was Month 36 (Week 156), Day 1 in the OLE Period will occur on the same day (since study drug is not administered as part of the Month 36 DB visit).

- The period of DB exposure, defined as the duration prior to first exposure to open-label treatment, will be 144 to 156 weeks (33 to 36 months).
- The primary analysis will be conducted after the last patient has completed the period of DB exposure or otherwise discontinued.

3. Open Label Extension (OLE) Period:

[figure not shown]
The study has been amended (Protocol Amendment 4) to include an OLE Period in lieu of the Open-Label Randomized Treatment Extension Period (previously introduced with Protocol Amendment 3). In the OLE Period, all patients will receive the vutrisiran 25 mg q3M regimen for up to 2 years. Patients initially randomized to **CCI** in the OLE Period (under Amendment 3) will transition to receive open-label doses of 25 mg q3M vutrisiran administered as SC injections at their next scheduled dosing visit.

4. Follow-Up Period:

Following completion of the OLE Period or completion of the DB Period for patients who do not continue into the OLE period or early treatment discontinuation in DB or OLE, patients will be followed up to 1 year after their last dose of study drug (up to 18 months for women of child-bearing potential).

Refer to Protocol Section 3.1 for more details.

Figure 1: Study Design

Abbreviations: DB=double-blind; OLE=open-label extension; q3M=every 3 months; **CCI** [REDACTED]; SC=subcutaneous.

Abbreviations: DB=double-blind; OLE=open-label treatment extension; q3M=every 3 months; SC=subcutaneous.

^a An individual patient's DB Period visits will end after they complete their Month 36 Visit, or 30 months after the last patient is randomized, whichever comes first. As such, a patient's last visit during the DB Period may vary from 30 to 36 months after enrollment (refer to Protocol Section 3.1).

^b The dosing schedule under Amendment 4 is 25 mg vutrisiran every 12 weeks. Upon entry into the OLE Period (OLE Day 1), all eligible patients will receive open-label doses of 25 mg q3M vutrisiran administered as SC injections. Patients initially randomized to receive **CCI** vutrisiran under Amendment 3 will transition to receive 25 mg q3M vutrisiran at their next scheduled dosing visit (24 weeks after their last dose of **CCI** vutrisiran).

^c Following completion of the OLE Period (or completion of the DB Period for patients who do not continue into the OLE Period; or their last dose of vutrisiran for patients who discontinue study drug early), patients will commence follow-up visits as outlined in Protocol Section 3.1. For women of child-bearing potential, the duration of the Follow-up Period will be up to 18 months from their last dose of study drug.

2.2. Objectives and Endpoints

Objectives	Endpoints
Primary	

To evaluate the efficacy of vutrisiran compared to placebo on reducing all-cause mortality and CV events	
Composite outcome of all-cause mortality and recurrent CV events (CV hospitalizations and urgent heart failure [HF] visits) in the overall populationComposite outcome of all-cause mortality and recurrent CV events (CV hospitalizations and urgent HF visits) in the vutrisiran monotherapy subgroup (defined as the group of patients not on tafamidis at study baseline)
Secondary	
To evaluate the efficacy of vutrisiran compared with placebo treatment on:
 
Functional capacityPatient-reported health status and health-related quality of lifeAll-cause mortalitySeverity of clinical heart failure symptoms 
The following secondary endpoints will be defined in both the overall population and the vutrisiran monotherapy subgroup:
 
Change from baseline in 6-MWTChange from baseline in the KCCQ-OSAll-cause mortalityChange from baseline in NYHA Class
Exploratory	
CCI [REDACTED]	
CCI [REDACTED]

Objectives	Endpoints

 • CCI 	
 • CCI
Pharmacodynamics and Pharmacokinetics	

 • To characterize the PD effect of vutrisiran on TTR • To characterize plasma PK of vutrisiran • To assess presence of antidrug antibodies (ADA) against vutrisiran 	
 • Change from baseline in serum TTR levels • Plasma PK exposure parameters • Frequency and titers of ADA
Safety	

Objectives	Endpoints

To evaluate the safety and tolerability of vutrisiran in patients with ATTR amyloidosis with cardiomyopathy	
Frequency of AEs

2.3. Study Procedure

Schedule of Assessments is included in Tables 1 and 2 in the Protocol.

2.4. Randomization Methodology

Using the interactive response technology (IRT), patients will be randomized 1:1 to the vutrisiran or placebo arm. Randomization will be stratified by:

- Baseline tafamidis use (yes vs. no)
- ATTR disease type (hATTR vs. wtATTR amyloidosis with cardiomyopathy)
- NYHA Class I/II **and** age < 75 years at baseline vs. all other

2.5. Blinding

[figure not shown]
Randomization schedule is maintained by the IRT vendor which has controlled access. During the DB Period, investigators, study personnel, and the Sponsor will remain blinded to treatment assignment and any clinical laboratory results that could potentially unblind them, including TTR levels, vitamin A levels, PK data, and ADA, until after the database lock for the primary analysis.

[figure not shown]
An independent external data monitoring committee (DMC) and an independent external biostatistics group supporting the DMC, and Sponsor and contract research organization personnel responsible for unblinded Suspected Unexpected Serious Adverse Reaction (SUSAR) reporting to regulatory agencies will have access to patient-level treatment assignment on a need-to-know basis.

Any unplanned unblinding occurring during the DB Period will be documented and reported in the CSR. During the OLE period, vutrisiran will be administered in an open-label fashion. Details about the specifics of the blinding aspects throughout the entire study are available in the Randomization and Blinding Plan.

2.6. Determination of Sample Size

Enrollment (randomization) of 600 patients was planned CCI

3. ANALYSIS POPULATIONS

The populations (analysis sets) are defined as follows:

- Full Analysis Set (FAS): All randomized patients who received any amount of study drug. Primary efficacy analyses will be based on the FAS. Patients in the FAS will be analyzed according to the treatment to which they were randomized.
- Vutrisiran Monotherapy Subgroup FAS (mono-FAS): All patients who were not on tafamidis at the study baseline in the FAS. Patients will be analyzed according to the treatment to which they were randomized.
- Safety Analysis Set (SAF): All patients who received any amount of study drug. Safety analyses will be based on the SAF. Patients will be analyzed according to the treatment received. Patients who were randomized to placebo group but received any amount of vutrisiran during the DB period will be grouped into the vutrisiran arm.
- Vutrisiran Monotherapy Subgroup Safety Analysis Set (mono-SAF): All patients who were not on tafamidis at the study baseline in the SAF. Patients will be analyzed according to the treatment received.
- PK Analysis Set: All patients who received at least 1 full dose of study drug and have at least 1 post dose blood sample for PK parameters and have evaluable PK data. Patients will be analyzed according to the first treatment received.

- PD Analysis Set: All patients who received at least 1 full dose of study drug and have an evaluable baseline and at least one evaluable postbaseline sample for TTR assessment. Patients will be analyzed according to the first treatment received.
- All Vutrisiran Treated Set: All patients who received any amount of vutrisiran during the study, including patients who took vutrisiran during the DB period and patients who first took placebo during the DB period and switched to vutrisiran during the OLE period.
- Vutrisiran Monotherapy Subgroup All Vutrisiran Treated Set: All patients who were not on tafamidis at the first dose of Vutrisiran in All Vutrisiran Treated Set.

4. GENERAL STATISTICAL CONSIDERATIONS

Categorical variables will be summarized using counts and percentages. Continuous variables will be summarized using the following descriptive summary statistics: number of patients (n), mean, standard deviation (SD), median, first quartile (Q1), third quartile (Q3), minimum, and maximum.

The day of the first dose of study drug administered is defined as Day 1. The Study Day of a time point of interest is calculated as follows.

If on or after Day 1, Study Day = date of interest – date of the first dose of study drug + 1

If prior to Day 1, Study Day = date of interest – date of the first dose of study drug

There is no Day 0. For example, the day before the first study drug dosing is defined as Day -1.

For laboratory parameters, if there are multiple assessments on the same day, the average will be calculated. Assessment results reported with mathematic symbol (e.g., >, <, =) will be replaced by the numeric value without mathematic symbol.

For 6-MWT, only assessments confirmed as valid by the Colorado Prevention Center (6-MWT site training and oversight vendor) will be included in analyses.

For efficacy analysis, heart transplant and LVAD placement will be treated as death, unless noted otherwise.

In general, all analyses will be presented by treatment groups in the overall population, vutrisiran monotherapy subgroup and background tafamidis subgroup. All listings will include all data collected during the entire study for all randomized patients. Due to large file size, listings will not be generated for individual KCCQ, CCI, mBMI, CCI, vital signs, and ophthalmology.

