6.5.5. Clinical Laboratory Assessments

Clinical laboratory assessments are listed in Table 6 and will be assessed as specified in the Schedules of Assessments (Table 1 and Table 2). These assessments will be evaluated by a central laboratory unless otherwise indicated.

LFTs must be reviewed by the Investigator prior to each dose of study drug.

Dosing decisions may be made based on LFT results (Table 6) collected at the previous dosing visit (up to 14 weeks prior to dosing); in all cases the most recently available LFTs should be used. Specific instructions for transaminase elevations are provided in Section 6.5.5.4.

For any other unexplained clinically relevant abnormal laboratory test occurring after study drug administration, the test should be repeated and followed up at the discretion of the Investigator, until it has returned to the normal range or stabilized, and/or a diagnosis is made to adequately explain the abnormality. Additional safety laboratories and assessments as indicated by the clinical situation may be requested.

While local laboratory results may be used for urgent clinical and dosing decisions, on the day of assessments all laboratory assessments specified in Table 6 which are performed at the clinic or outside the clinic (eg, the patient's home), should also be sent in parallel to the central laboratory. In the case of discrepant local and central laboratory results on samples drawn on the same day, central laboratory results will be relied upon for clinical and dosing decisions. The only exception for central laboratory testing is related to the COVID-19 pandemic as described in the beginning of Section 6.

For any safety event or laboratory abnormality, additional laboratory assessments, imaging, and consultation may be performed for clinical evaluation and/or in consultation with the Medical Monitor; results may be collected and should be included in the clinical database.

Table 6: Clinical Laboratory Assessments

Hematology	
Complete blood count with differential	
Serum Chemistry	
Sodium	Potassium
BUN	Phosphate
Uric acid	Albumin
Total protein	Calcium
Glucose	Carbon dioxide
Creatinine CCI	Chloride
Bicarbonate	
Liver Function Tests	
AST	ALP
ALT	Bilirubin (total and direct)
GGT	
Additional Chemistry Assessments	
C-reactive protein	Venous lactate
Urinalysis	
Visual inspection for appearance and color	Bilirubin
pH (dipstick)	Nitrite
Specific gravity	RBCs
Ketones	Urobilinogen
Albumin	Leukocytes

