5.11. Safety Analyses

For AEs, CMs, procedures, laboratory parameters, vital signs and body weight, and ECG, summaries will be based on data from the date of first dose of study drug through the first dose in the OLE period for patients who entered OLE, or through 84 days after the last dose of study drug for patients who discontinued or completed DB treatment.

For by-visit summaries of safety parameters, only scheduled visits and central laboratory data will be used. For derivation of worst postbaseline values and abnormalities, all available assessments (i.e., scheduled and unscheduled) will be used. For the selected laboratory parameters (such as LFTs), two sets of deviations will be used to determine the worst postbaseline values. One set will be solely using central laboratory data and the other set will make use of both central and local laboratory data.

No inferential safety analysis is planned.

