5.11.2. Laboratory Data

Clinical laboratory values will be expressed in standard units. Missing laboratory data will not be imputed.

For each continuous clinical laboratory parameter (including hematology, serum chemistry, liver function tests (LFTs), coagulation, and urinalysis), descriptive statistics will be presented for the actual values, change from baseline, and percentage change from baseline by visit, or average of multiple records per visit will be presented. These by-visit tables for the DB period will use the central laboratory data only.

For hematology and serum chemistry, summary tables of potentially clinically significant abnormalities will be provided. The results may also be graded according to the National Cancer Institute CTCAE Version 5.0 or above. A shift summary of baseline to maximum postbaseline CTCAE grade may be presented during the DB period, as appropriate. For shift and summary of

abnormalities in worst post-baseline tables, the central laboratory data will be used. For the selected laboratory parameters (such as LFTs), the abnormalities tables and figures using both central and local laboratory data will be presented as applicable.

CCI

All laboratory data will be provided in data listings. Laboratory results with CTCAE grade 3 or higher will be presented in a separate listing with proper flags. Local laboratory data, if available, will also be flagged.

Liver Function Tests

A frequency table and a shift table will be produced to summarize the number and percentage of patients in each of the below categories at any postbaseline time point.

- Alanine aminotransferase (ALT): $>1 \text{ & } \leq 3$, $>3 \text{ & } \leq 5$, $>5 \text{ & } \leq 10$, $>10 \text{ & } \leq 20$, $>20 \times$ upper limit of normal (ULN),
- Aspartate aminotransferase (AST): $>1 \text{ & } \leq 3$, $>3 \text{ & } \leq 5$, $>5 \text{ & } \leq 10$, $>10 \text{ & } \leq 20$, $>20 \times \text{ULN}$,
- ALT or AST: $>1 \text{ & } \leq 3$, $>3 \text{ & } \leq 5$, $>5 \text{ & } \leq 10$, $>10 \text{ & } \leq 20$, $>20 \times \text{ULN}$,
- Alkaline phosphatase (ALP): ≤ 1 , $>1 \text{ & } \leq 1.5$, $>1.5 \times \text{ULN}$,
- Total Bilirubin: ≤ 1 , $>1 \text{ & } \leq 1.5$, $>1.5 \text{ & } \leq 2$, $>2 \text{ & } \leq 3$, $>3 \text{ & } \leq 5$ and $>5 \times \text{ULN}$,
- Total Bilirubin $> 2 \times \text{ULN}$ concurrent with ALT or AST $> 3 \times \text{ULN}$

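### The same-day averaging rule in SAP Section 4 has no exception for worst values, so the supplementary central-plus-local liver tables can understate a peak

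*SAP*

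**What the plan says.** **The averaging rule.** SAP Section 4 (General Statistical Considerations) sets it for all laboratory data: "For laboratory parameters, if there are multiple assessments on the same day, the average will be calculated". Nothing there limits it to by-visit tables, to one laboratory, or to one scale (raw units or multiples of ULN).

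**Worst values.** SAP Section 5.11 says: "For derivation of worst postbaseline values and abnormalities, all available assessments (i.e., scheduled and unscheduled) will be used". For selected parameters such as LFTs it adds two derivations: "One set will be solely using central laboratory data and the other set will make use of both central and local laboratory data".

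**Which tables use which data.** SAP Section 5.11.2 assigns the main shift and worst-value outputs to the central laboratory: "abnormalities in worst post-baseline tables, the central laboratory data will be used". It then adds, for LFTs and similar parameters, that "the abnormalities tables and figures using both central and local laboratory data will be presented as applicable". LFT categories and peak plots are expressed as multiples of ULN. By-visit tables are central-only and carry their own mention of averaging several records per visit. All laboratory data are listed, with local results flagged.

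**Same-day pairs.** Protocol Section 6.5.5 lets sites use local results for urgent clinical and dosing decisions, but samples taken that day "should also be sent in parallel to the central laboratory". It also foresees disagreement: "In the case of discrepant local and central laboratory results on samples drawn on the same day, central laboratory results will be relied upon". That precedence covers clinical and dosing decisions and is not an analysis rule.

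**The concern.** Read together, these rules leave the order of operations open. Averaging by day first and then taking the worst daily value complies with both Section 4 and Section 5.11. For a peak this is the wrong order, because a mean cannot exceed the larger of its two inputs and so any error is downwards. The ULN adds a second difficulty. If the two laboratories have different limits, a mean of raw values has no ULN of its own to be divided by.

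The stake is the liver safety display. The protocol names LFT abnormality as an important potential risk (Section 1.7) and makes ALT or AST above 3x ULN an adverse event of clinical interest (Section 6.5.6.1). The same cut-off defines the combined bilirubin-and-transaminase category in SAP Section 5.11.2. Such elevations may be few: Protocol Section 1.4 reports two subjects above 3x ULN in Phase 1. One reclassified patient could then be visible in a table.

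**Working it through.** The plan gives no figure to reproduce and no ULN values. The ALT pairs, ULNs and degrees of disagreement below are assumptions chosen to show the mechanism.

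**Step 1. Where can averaging across laboratories occur?**
- Central-only derivation (main shift and worst post-baseline tables): no local value enters. Only duplicate central samples on one day could be averaged.
- Central-plus-local derivation (supplementary LFT tables and figures): a parallel local and central pair from one day can be averaged.

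**Step 2. What does averaging do to a pair?** Values are multiples of each laboratory's own ULN; mean = (central + local)/2.

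| Central | Local | Mean | Central-only set | Highest single result | Averaged combined set |
|---|---|---|---|---|---|
| 3.4 | 2.4 | 2.9 | above 3x | above 3x | not above 3x |
| 2.4 | 3.4 | 2.9 | not above 3x | above 3x | not above 3x |
| 5.4 | 4.2 | 4.8 | above 5x | above 5x | above 3x, up to 5x |
| 3.4 | 2.8 | 3.1 | above 3x | above 3x | above 3x |

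In rows 1 and 3, adding local data lowers the category that central data alone would give. In row 2 the local elevation is lost from the set that was meant to include local data. Row 4 shows that not every pair is affected.

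**Step 3. How high a peak can be hidden?** Let the higher result be H and the lower one H(1 - d). The mean is H(1 - d/2), which is at or below 3 whenever H is at or below 3/(1 - d/2).
- d = 5%: 3/0.975 = 3.08x
- d = 10%: 3/0.95 = 3.16x
- d = 20%: 3/0.90 = 3.33x
- d = 30%: 3/0.85 = 3.53x

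With small disagreement, only values just above the cut-off are at risk.

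**Step 4. What does a different ULN add?** Take the same raw ALT of 128 U/L from both laboratories, with a central ULN of 40.
- Central multiple: 128/40 = 3.20x.
- Local ULN 45: 128/45 = 2.84x; mean of multiples (3.20 + 2.84)/2 = 3.02x.
- Local ULN 55: 128/55 = 2.33x; mean of multiples (3.20 + 2.33)/2, about 2.76x.

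If raw values are pooled instead, the mean is 128 U/L. That is 3.20x, 2.84x or 2.33x depending on which ULN is attached, and the SAP does not say which.

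**Step 5. When does it change a patient's worst value?** Only if the paired day holds that patient's peak. A higher result on another day would still set the category.

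**The case against.** The strongest reply is that the specific rule overrides the general one: Section 5.11 uses all available assessments for worst values, and the mention of averaging in by-visit tables shows where averaging belongs. This is a reasonable reading and may be what the authors intend. It does not settle the matter, because Section 5.11 explains its phrase only in terms of scheduled and unscheduled assessments and says nothing about same-day replicates. SAP Section 1 places table specifications in separate documents, which may resolve the point but are not available here.

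A reader might infer that peak ALT and AST are diluted across laboratories throughout the safety report. The documents do not support that, since the main shift and worst post-baseline tables are central-only.

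A reader might also infer that true elevations would vanish from the record. They would not. Individual results are listed with local values flagged, and ALT or AST above 3x ULN is separately captured and reported as an adverse event of clinical interest (Protocol Sections 6.5.6.1 to 6.5.6.3).

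Nor do the documents say that same-day pairs arise mainly when transaminases are high. Protocol Section 5.2.4 asks for central confirmation of an elevation above 3x ULN ideally within 2 to 3 days and no later than 7. Such a repeat will often fall on another day, outside the averaging rule. These limits on scope stand.

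**Conclusion.** The point holds for the supplementary central-plus-local LFT tables and figures and, to a smaller degree, for duplicate central samples on one day. There the SAP permits a derivation that can only lower a peak, lacks a defined ULN multiple if raw values are pooled, and can make the combined set less sensitive than the central-only set. For two results that differ by 5% to 30%, peaks up to about 3.1x to 3.5x ULN could fall out of the above-3x category.

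That range rests on assumed disagreement, and the examples rest on assumed ULNs. The documents give no frequency of same-day pairs, so the number of patients affected cannot be estimated. No efficacy result or Type I error rate is touched. Severity is minor.

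**What to change.** Add one sentence to SAP Section 4 or 5.11. Same-day averaging applies only to by-visit descriptive summaries and only within one laboratory. Worst post-baseline, shift, CTCAE grade, LFT category, bilirubin-with-transaminase and peak-plot derivations use the worst individual result, with each LFT expressed as a multiple of the ULN of the laboratory that produced it. Results are never averaged across laboratories.

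The cost is that sentence and a small programming check; no new data are needed, provided each local result is stored with its own ULN. If the database is already locked, record the change and its justification in the clinical study report, as SAP Section 1 provides.
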